### **Supportive Analysis no. 1:**

An ANOVA model for repeated measures will be performed with treatment group and region as covariates. Missing data will be imputed using linear interpolation for assessments at Week 4 and linear extrapolation for assessments at Week 12.

The LSMEANS estimate of MRI score, difference of the LS Mean from placebo, 2-sided 95% CI of the difference and nominal 2-sided p-value of the difference from the model contrast will be presented at each visit.

Validity of the model will be verified as follows:

- Repeated-measures designs have the assumption of Sphericity which means that the variance of the population difference scores for any two conditions should be the same as the variance of the population difference scores for any other two conditions. This assumption can be tested using the Mauchly's sphericity test (available with GLM SAS procedure).
- Normality of residuals by timepoint will be checked by computing Skewness and Kurtosis, which should fall within the interval [-2;2]. Normal QQ-plot of residuals will be performed as well.

An example of SAS code is available in Appendix 18.5.

In addition, summary statistics of observed values, change and percent change from baseline will be presented at each visit for each treatment group.

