### 7.3.3 Prevention of Joint Structural Damage Progression

Joint structural damage will be assessed using MRI at Baseline and Weeks 4 and 12 in subjects participating in the MRI substudy.

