**MMRM:**

The MAR are ignorable missingness. When missing data due to dropout are ignorable, the parameters of dropout and outcome processes are assumed to be distinct. Hence, likelihood-based methods can be used on the marginal distribution of the observed data for statistical inference. MMRM is a particular form of a mixed model analysis and is fitted within the ignorable likelihood paradigm.

The MRI endpoints (change from baseline) will be analyzed using the MMRM model, with treatment group, visit, and treatment by visit interaction as the main effects, baseline MRI assessment and region as covariates. The unstructured covariance matrix will be considered. Denominator degree of freedom will be computed using Kenward and Roger’s method (Kenward 1997).

The LSMEANS estimate of MRI mean change from baseline score, difference of the LS Mean from placebo, 2-sided 95% CI of the difference and nominal 2-sided p-value of the difference from the model contrast will be presented at each visit.

An example of SAS code is available in Appendix 18.5.

In addition, summary statistics of observed values, change and percent change from baseline will be presented at each visit for each treatment group.

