### **Supportive Analysis no. 2:**

A similar analysis as the supportive analysis no. 1 will be performed, but this time data will not be imputed.

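### Neither supportive ANOVA for the RAMRIS scores tests the primary MMRM's missing-data assumption on its own, and the Week 12 extrapolation in no. 1 is not a conservative stress test

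*SAP*

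**What the plan says.** Protocol Section 8.5.3.3 specifies a mixed model for repeated measures for the MRI change scores, with baseline as a covariate and missing data treated as missing at random. It promises other imputation methods as sensitivity analyses.

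SAP Section 14.2.3 then gives three analyses of the RAMRIS scores:

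- **Primary MMRM.** The outcome is change from baseline. The terms are treatment, visit and treatment by visit, with "baseline MRI assessment and region as covariates". The covariance is unstructured.
- **Supportive no. 1.** "An ANOVA model for repeated measures will be performed with treatment group and region as covariates". The output is described as "The LSMEANS estimate of MRI score". On missing values: "Missing data will be imputed using linear interpolation for assessments at Week 4 and linear extrapolation for assessments at Week 12". For the model check: "This assumption can be tested using the Mauchly's sphericity test".
- **Supportive no. 2.** "A similar analysis as the supportive analysis no. 1 will be performed, but this time data will not be imputed".

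On timing, Protocol Section 7.3.3 states: "Joint structural damage will be assessed using MRI at Baseline and Weeks 4 and 12 in subjects participating in the MRI substudy". The SAP does not say which points anchor the extrapolation, or whether nominal or actual scan dates are used.

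**The concern.** A sensitivity analysis for missing data is easiest to interpret when only the missing-data handling changes. As written, no. 1 differs from the primary analysis in outcome scale, covariates and imputation together. No. 2 differs mainly in the model. If either disagreed with the MMRM, a reader could not tell whether missing data, lost precision or chance baseline imbalance was the cause.

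The imputation itself also leans one way. A subject who improves by Week 4 and then has no Week 12 scan is assigned continued improvement at the same rate. That usually favours an active drug, whereas a stress test should ask what happens if such subjects did worse than the model expects. The MRI section has no analysis of that kind, although the SAP plans one for ACR20 (Section 14.1, supportive analysis no. 4).

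**Working it through.** **The plan's own MRI figures.** Protocol Section 8.1 gives 40 evaluable subjects per arm, an effect size of 0.7 for change, two-sided alpha 0.05, about 80% power by Wilcoxon rank-sum (about 70% at 0.6), and 45 enrolled for about 11% loss.

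- Enrolment: 40 / 0.89 = 44.9, so 45. Reproduced.
- Power: a t-test with n multiplied by the lower-bound Wilcoxon efficiency of 0.864 gives 81.8% at 0.7 and 69.1% at 0.6. Reproduced within 2 points. The plain t-test gives 87.1% and 75.5%.

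**Extrapolation factor.** Scans exist only at Baseline, Week 4 (Day 28) and Week 12 (Day 84), so a missing Week 12 value can be extrapolated only from the first two. With the baseline scan on day t0, the imputed change is the Week 4 change times (84 − t0) / (28 − t0).

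| Baseline scan | Factor | Variance multiplier |
|---|---|---|
| Nominal 0 | 84/28 = 3.00 | 9.0 |
| Day 1 | 83/27 = 3.07 | 9.4 |
| Day −7 (protocol limit, Table 1 footnote) | 91/35 = 2.60 | 6.8 |
| Day −35 (edge of SAP Table 51 window) | 119/63 = 1.89 | 3.6 |

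**Effect on the estimate.** Let m be the fraction extrapolated, equal across arms and missing completely at random, and f the share of the Week 12 effect already present at Week 4. With factor 3:

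estimate / truth = (1 − m) + m × 3 × f

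With m = 0.11 (taken from the planned loss) and f assumed:

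- f = 1/3 (linear growth): 0.89 + 0.11 = 1.00
- f = 1/2: 0.89 + 0.165 = 1.06
- f = 1: 0.89 + 0.33 = 1.22

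At f = 1 the ratio is 1.10 for m = 0.05 and 1.40 for m = 0.20. Inflation arises only when f exceeds 1/3.

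A simulation (45 per arm, 11% of Week 12 missing completely at random, correlations 0.5 to 0.9) agrees. With change analysed and no baseline covariate, the standard error is 0.31–0.32 of the true effect on observed data and 0.41–0.43 with extrapolation. A baseline-adjusted MMRM-type estimator gives 0.27–0.31, with an estimate close to the truth.

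**Omitting the baseline covariate.** Let ρ be the baseline-to-Week-12 correlation, with equal SDs. The documents give no ρ, so these values are assumed. An effect of 0.7 SD of change equals 0.7 × √(2(1 − ρ)) SD of the raw score. Relative to the baseline-adjusted analysis, the variance is multiplied by 1/(1 − ρ²) for raw scores and by 2/(1 + ρ) for change scores. Power is from the noncentral t, 40 per arm:

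| ρ | Variance ratio, raw | Variance ratio, change | Power, adjusted | Power, change only | Power, raw only |
|---|---|---|---|---|---|
| 0.7 | 1.96 | 1.18 | 92% | 87% | 67% |
| 0.8 | 2.78 | 1.11 | 90% | 87% | 50% |
| 0.9 | 5.26 | 1.05 | 89% | 87% | 28% |

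**The case against.** **The two ANOVAs can show something about missing data.** A reader might infer that they are uninformative. The documents do not support that: nos. 1 and 2 share one model and differ only in imputation, so their contrast isolates the effect of the extrapolation. This stands. What remains missing is a test of the primary MMRM's own assumption, and any analysis of a plausible departure from it.

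**The visible text does not settle the ANOVA.** A reader might infer that baseline is discarded altogether. The covariate list also omits visit, yet results are required at each visit, so the sentence is not the full model. Mauchly's test is informative only with three or more repeated levels, which suggests that baseline may be a level of the response. The sample code in Appendix 18.5 is redacted, and that is not a fault of the plan. If the model is fitted by GLM, which the SAP names for the sphericity test, subjects with a missing visit may also be dropped, making no. 2 a complete-case analysis. This stands: only the absence of baseline as a listed covariate is certain.

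**The large power losses need a raw-score outcome.** Section 14.2.3 lists the endpoint as change from baseline, so MRI score may be shorthand. On change scores the loss is only 2 to 5 points. The 67%, 50% and 28% figures are conditional on the other reading and on assumed correlations.

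**Few values may need extrapolating.** MRI is scheduled at the early-withdrawal visit, and SAP Table 51 counts a scan on Days 56 to 98 as Week 12. Late leavers may thus have an observed value, so 11% is an assumption that may be too high.

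**Conclusion.** The point holds in limited form. As written, neither supportive ANOVA varies only the missing-data assumption of the primary MMRM, and none of the three analyses probes an unfavourable departure from missing at random.

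The extrapolation is roughly a tripling of the Week 4 change: exactly 3 on nominal days and about 1.9 to 3.1 with actual scan dates. The tripling is an inference from the schedule; the SAP does not state it. With 11% extrapolated on the nominal schedule, the effect is inflated by 0% to 22% for growth ranging from linear to complete by Week 4.

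The cost of omitting baseline depends on the outcome scale: small for change scores, large for raw scores.

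Severity is low to moderate. RAMRIS scores are other secondary endpoints, SAP Section 14.2 calls the secondary analyses supportive with nominal p-values, and the ACR20 conclusion is not affected.

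**What to change.** - **Supportive no. 1:** analyse change from baseline with the MMRM mean model (baseline score, region, treatment, visit, treatment by visit), so that only the missing-data handling differs from the primary analysis. Replace the Week 12 extrapolation with the control-based multiple imputation already planned for ACR20. If the extrapolation is kept, show it only as an extra row, and state its anchor points and whether nominal or actual dates are used.
- **Supportive no. 2:** if kept, add the baseline score as a covariate, state the outcome scale, and present it as a check of the model, not of missing data. It should not be given the full MMRM mean model, because on observed data that would nearly duplicate the primary analysis.

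The cost is a little extra programming. No new data are needed, since the baseline score is already collected.

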### **Supportive Analysis no. 2:**

A similar analysis as the supportive analysis no. 1 will be performed, but this time data will not be imputed.

### **Lineplot:**

Mean score CFB will be presented as a by-visit line plot for each treatment group, with all treatment groups included in a single figure, and horizontal axis extending to Week 12 (RAMRIS Synovitis and Osteitis only).

#### 14.2.4 HRQoL Endpoints at Week 12

The following HRQoL endpoints will be presented on QoL analysis set:

- HAQ-DI
- SF-36
- FACIT-Fatigue

CCI [Redacted]

HAQ-DI scoring is detailed in Appendix 18.2.

A full description of the scoring rules of each health concept of SF-36 as well as Physical Component Summary (PCS) and Mental Component Summary (MCS) is available in Appendix 18.3.

A full description of the scoring instructions of FACIT-Fatigue scale is available in Appendix 18.4.

CCI [Redacted]

**Table 18 : Analysis of HRQoL Endpoints at Week 12**

Endpoints	Analysis Set	Analysis method	Missing data handling

 
• HAQ-DI Total Score
 
	
 
• QoL set
 
	
 
• MMRM
 
	As observed

 
• SF-36 (Change in PCS, MCS scores, and their components)
 
• FACIT-Fatigue (Change in Total score over time)
 
 
CCI [Redacted]
	
 
• QoL set
 
	
 
• MMRM model
 
• Descriptive statistics
 
• Probability of achieving %CFB value or higher
 
• Logistic regression
 
	As observed

**MMRM model:** similar as in Section 14.2.3.

### **Descriptive statistics:**

For each treatment group, descriptive statistics will be presented for absolute value, CFB and percent CFB value for each visit, from baseline to Week 12.

In addition, for each SF-36 endpoint (domain scores, MCS, PCS), FACIT-Fatigue Total Score and CCI, the following will be provided:

- the number (proportion) of subjects not worsening, and number (proportion) of subjects worsening, between baseline and Week 12 by treatment group. Worsening is defined as a decrease of 5 for SF-36 endpoints and FACIT-Fatigue Total Score, and as an increase of 5 for CCI.
- Mean score over time will be presented as a by-visit bar plot for each treatment group, with all treatment groups included in a single figure, and horizontal axis extending to Week 12.

In addition, for the CCI, the frequency of item administration by visit will be reported (ie, the items that were selected and administered by the CAT algorithm).

### **Probability of achieving %CFB value or higher:**

For each SF-36 endpoint (domain scores, MCS, PCS), a figure will be provided describing the distribution of % CFB at Week 12, one curve per treatment group. The curve will display proportion of subjects having a value for % CFB > x at Week 12, where the range of x depends on the data.

The same will be applied for FACIT-Fatigue Total Score and CCI.

### **Logistic regression:**

Response on the SF-36 (PCS, PF, VT), FACIT-Fatigue total score and CCI will be further analyzed based on differences in proportion of responders, comparing each dose of evobrutinib versus placebo.

Responder definitions will be based on minimal clinically important difference (MCID) criteria for improvement or deterioration as follows:

- SF-36 - PCS:
  - Improvement is defined as an increase greater or equal to 2.5 compared to baseline
  - Deterioration is defined as a decrease greater or equal to 0.8 compared to baseline
- SF-36 – domain scores:
  - Improvement is defined as an increase greater or equal to 5.0 compared to baseline
  - Deterioration is defined as a decrease greater or equal to 2.5 compared to baseline
- FACIT-Fatigue Total Score:
  - Improvement is defined as an increase greater or equal to 4.0 compared to baseline

- Deterioration is defined as a decrease greater or equal to 4.0 compared to baseline

CCI

Logistic regression model for repeated measures will be applied, with adjustments for the region, baseline value and with treatment as a factor. An example of SAS code is available in Appendix 18.5.

### 14.2.5 Exploratory Efficacy Endpoints at Week 12

CCI

CCI

### 14.3 Subgroup Analysis

The following subgroup analyses will be considered:

- Region (Western Europe, US, ROW)
- MRI substudy participation (Yes, No)
- Gender (Male, Female)

The endpoints at Week 12 and the statistical analysis method are described in [Table 21](#).

To assess numerically the consistency of each endpoint among subgroups of subjects, the analysis will be performed on the mITT Analysis Set for each modality using a logistic regression model. The interaction between treatment group and subgroup of interest will be calculated as well. Logistic models to be performed are summarized in [Table 20](#).

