## 2 Sponsor, Investigators and Trial Administrative Structure

This clinical trial will be sponsored by:

- EMD Serono Research & Development Institute, Inc., Billerica, Massachusetts, USA, in the USA.
- Merck Serono Co., Ltd., (Affiliate of Merck KGaA, Darmstadt, Germany) in Japan.
- Merck KGaA, [name] in countries outside the USA and Japan.

Study Organization in Japan: Refer to Study Organization in Japan in supporting documentation for additional information.

The trial will be conducted at approximately 160 sites in the USA (15 sites), Europe, South America, Africa, and Japan. The Coordinating Investigator, PPD [REDACTED], represents all Investigators for decisions and discussions regarding this trial, consistent with the International Council for Harmonisation (ICH) Topic E6 Good Clinical Practice (GCP; hereafter referred to as ICH GCP). The Coordinating Investigator will provide expert medical input and advice relating to trial design and execution and is responsible for the review and signoff of the clinical trial report (CTR).

Trial Sites in Japan: Refer to the Trial Sites in Japan supporting documentation.

An Independent Data Monitoring Committee (IDMC) will be established to continually review available data and safeguard the interests of trial subjects. The IDMC will be composed of a minimum of 3 members who do not have any conflicts of interest with the trial Sponsor, and are not Investigators for this study, or any other study of evobrutinib in rheumatoid arthritis, including 2 clinicians and a biostatistician. The full membership, mandate, and processes of the IDMC will be detailed in the IDMC Charter.

In addition, the trial will be advised and monitored by a Study Steering Committee, chaired by the Coordinating Investigator and comprised of, at minimum, 3-5 Study Investigators, the Clinical Program Lead, and the Medical Responsible. Recommended optional members of the Study Steering Committee include the Study Statistician and the Operational Lead from the contract research organization (CRO). Signature pages for the Protocol Lead and the Coordinating Investigator as well as a list of Sponsor responsible persons are provided in [Appendix III](#).

The trial will appear in the following clinical trial registries: [clinicaltrials.gov](http://clinicaltrials.gov) and [www.clinicaltrialsregister.eu](http://www.clinicaltrialsregister.eu).

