**Table 20 : Logistic regression models for subgroup analysis**

Subgroup	Subjects to be included in the model	Main effects	Result to be presented in TLFs
• Region	• All subjects from mITT Set	• Treatment, region and treatment by region interaction	P-value from the interaction between treatment and region
	• Subjects from mITT Set – Region=Western Europe	• Treatment	From comparison with placebo: • Estimated OR, • Two-sided 95% CI of the estimated OR
	• Subjects from mITT Set – Region=US	• Treatment	
	• Subjects from mITT Set – Region=ROW	• Treatment	
• MRI substudy participation	• All subjects from mITT Set	• Treatment, MRI substudy participation and treatment by MRI substudy participation interaction	P-value from the interaction between treatment and MRI substudy participation
	• Subjects from mITT Set – MRI substudy participants only	• Treatment, region	From comparison with placebo: • Estimated OR, • Two-sided 95% CI of the estimated OR
	• Subjects from mITT Set – MRI substudy non-participants only	• Treatment, region	
• Gender	• All subjects from mITT Set	• Treatment, gender and treatment by gender interaction	P-value from the interaction between treatment and gender
	• Subjects from mITT Set – females	• Treatment, region	From comparison with placebo: • Estimated OR, • Two-sided 95% CI of the estimated OR
	• Subjects from mITT Set – males	• Treatment, region	

The same missing data imputation approach will be used as the primary analysis method. An example of SAS code is available in Appendix 18.5.

In addition, a forest plot will be presented for each endpoint for the overall treatment effect and within each subgroup of interest including OR from logistic model and associated 2-sided 95% CI of OR.

Summary tables will be presented for each endpoint by subgroup, comparing each evobrutinib dose group vs placebo.

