**Table 21 : Subgroup Analysis – Endpoints**

Endpoints	Analysis	Analysis method	Description	Missing data handling

 
• ACR 20/50/70
 
• DAS28-hsCRP < 2.6
 
• DAS28-hsCRP < 3.2
 
• EULAR Boolean Remission
 
• CDAI ≤ 2.8
 
• SDAI ≤ 3.3
 
• EULAR Responder Index [good/moderate, vs no response]
 
	
 
• Week 12
 
	Logistic regression	Presentation of response rate for each treatment group, Δ in response rate compared to placebo, 2-sided 95% CI of Δ (non-stratified MN), OR, 2-sided 95% CI of OR, p-value of interaction between treatment and subgroup of interest	LOCF-NR*

\* LOCF-NR: post-baseline last observation carried forward. At Week 12, patients who discontinued from treatment are considered as non-responders.

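### The subgroup logistic models have no rule for empty treatment-by-subgroup cells, which are likely for the rare remission endpoints in a small region and can make a Wald interaction p-value look like consistency

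*SAP*

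**What the plan says.** SAP 14.3 sets out to check numerically whether effects agree across subgroups: "the analysis will be performed on the mITT Analysis Set for each modality using a logistic regression model". For region, Table 20 fits "Treatment, region and treatment by region interaction" and reports the "P-value from the interaction between treatment and region". MRI participation and gender are handled in the same way. Within each level the output is an odds ratio against placebo with its interval. Each endpoint also gets a forest plot, overall and "within each subgroup of interest including OR from logistic model and associated 2-sided 95% CI of OR".

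Table 21 lists nine binary endpoints: ACR20/50/70, DAS28-hsCRP < 2.6 and < 3.2, "EULAR Boolean Remission", CDAI and SDAI remission, and EULAR response. Its footnote adds that "At Week 12, patients who discontinued from treatment are considered as non-responders", which lowers responder counts further. The same table asks for response rates and the difference from placebo with a "2-sided 95% CI of Δ (non-stratified MN") interval.

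The one readable logistic example in SAP Appendix 18.5 is a plain PROC LOGISTIC main-effects call, without a Firth, exact or profile-likelihood option. The readable text sets no minimum responder count and no rule for separation. SAP 9.6 says only that statistics that cannot be calculated are shown as NE. Protocol 8.5.4.7 describes all subgroup analyses as descriptive and aimed mainly at consistency.

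**The concern.** Maximum-likelihood logistic regression has no finite odds ratio when one arm of a comparison has no responders. If placebo is empty in a subgroup, every dose-versus-placebo odds ratio there is infinite. If only a dose arm is empty, its odds ratio is zero. If both are empty, it is undefined. Software usually still prints a number: a very large coefficient with an enormous standard error that depends on where the iterations stopped.

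The interaction test is affected in one direction. A Wald test divides the diverging coefficient by its larger standard error, so the p-value drifts upwards. Since the stated purpose is to judge consistency, a high p-value that comes from an empty cell can be misread as evidence that the effect is the same across regions, sexes or MRI groups.

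**Working it through.** **Inputs from the documents.** There are 80 evaluable subjects per arm with 11% loss (SAP 8.2.1). Dividing 80 by 0.89 gives 89.9, which reproduces the plan's 90 per arm. Allocation is 1:1:1:1. About 45 per arm are in the MRI substudy (Protocol 8.2). The protocol gives "approximately 160 sites in the USA (15 sites") as the US share of sites. SAP Table 3 has three regions.

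**Assumptions.** The documents give no remission rates, so placebo/evobrutinib pairs from 2%/5% to 10%/20% are used. US enrolment is taken as proportional to sites: 90 times 15/160 is 8.4, about 8 per arm. The documents do not give the sex split; 18 per arm stands for an assumed 20% minority sex (20% of 90).

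**Formula.** For one subgroup level with n per arm, P(at least one of four arms empty) = 1 − [1 − (1 − pP)^n] × [1 − (1 − pE)^n]^3.

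Example, n = 8 at 10%/20%. The placebo term 0.90^8 is 0.430 and the evobrutinib term 0.80^8 is 0.168. The chance that no arm is empty is therefore 0.570 times 0.832^3, which is 0.33, and the chance of at least one empty arm is 0.67.

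| Assumed rates (placebo/evobrutinib) | n = 8 (US) | n = 18 (minority sex) | n = 45 (one MRI level) |
|---|---|---|---|
| 2%/5% | 99% | 93% | 56% |
| 5%/10% | 94% | 63% | 12% |
| 8%/15% | 81% | 34% | 3% |
| 10%/20% | 67% | 20% | 1% |
| ACR20 at 30%/60% | 6% | 0.2% | 0% |

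The chance that placebo itself is empty in the US, which removes all three comparisons there, is (1 − pP)^8, that is 85%, 66% and 43% at placebo rates of 2%, 5% and 10%.

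An interaction model fails if any of its cells is empty. At 2%/5%, 5%/10% and 10%/20% the chances are:
- MRI (8 cells of 45): 81%, 23% and 2%.
- Gender (18 and 72 per arm): 95%, 64% and 20%.
- Region (assumed split of 10%, 20% and 70%): about 100%, 97% and 68%.

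**Effect on the interaction test.** Maximum-likelihood models were fitted to 1,000 simulated trials per scenario, at those three rate pairs for each factor, with no true interaction. The nominal 5% Wald test rejected in 0.0 to 2.9% of trials overall. Among trials with an empty cell it rejected in 0 to 0.15%, with median p from 0.67 to above 0.99. The likelihood-ratio test on the same data rejected in 3.8 to 9.4%. In one worked gender case (72 and 18 per arm, 0/18 on placebo in the smaller sex) the interaction coefficients were about 19.7 with standard error about 11,360. The Wald p-value was 0.99 and the likelihood-ratio p-value 0.62.

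**Effect on the odds ratio.** For 0/8 versus 2/8, one maximum-likelihood fit stopped at a log odds ratio of 21.5 with standard error about 17,000. With two groups the Firth estimate equals adding 0.5 to each cell. The odds are then 2.5 to 6.5 on evobrutinib against 0.5 to 8.5 on placebo, an odds ratio of 6.5. Its profile-likelihood 95% interval is 0.43 to 965.

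**The case against.** The case against is substantial.

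- **Status.** The analyses are descriptive and no decision rule uses these p-values. Table 21 prints each arm's response rate and a Miettinen-Nurminen interval, so a reader will see a 0% beside an odd odds ratio. The overall analyses of these endpoints (Tables 15 and 16) use Miettinen-Nurminen differences. This stands and limits the impact.
- **Redaction.** Section 14.3 points to example code in Appendix 18.5, much of which is blacked out, and Table 20 does not name the interaction test. Wald is the PROC LOGISTIC default, but the subgroup code may say otherwise. This stands as a caveat.
- **The NE rule.** It may catch some cases, but not reliably, because a separated fit usually returns finite, meaningless numbers.
- **Assumptions.** The rates are assumed, and the US share uses a site total that includes Japan, where SAP section 7 says no recruitment took place. For MRI the risk runs from negligible to about even at each level.

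A reader might infer that every subgroup odds ratio becomes infinite, that all interaction p-values are meaningless, or that the trial's main finding is at risk. The documents do not support this. An empty dose arm gives zero and affects one comparison only. The p-value failure belongs to the Wald test, with median p as low as 0.67 in some scenarios. ACR20 is barely touched, and the primary analysis does not use these models.

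**Conclusion.** The point holds in a limited form. For the rare Table 21 endpoints, the readable plan has no provision for empty cells in the Table 20 models. In a region as small as the US appears to be, an empty arm is the likely outcome over the whole assumed range (67 to 99%). For gender and MRI participation it depends on the true rates, with about 1 to 56% at 45 per arm. Where it happens, the odds ratio is infinite, zero or undefined, and a Wald interaction test almost never rejects, so a high p-value says little about consistency. The consequence is misleading forest plots and interaction p-values in descriptive output. The conclusion rests on the assumed remission rates, on US enrolment following sites, and on the redacted code not already using another method.

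**What to change.** For Boolean, CDAI and SDAI remission, DAS28 < 2.6 and ACR70, amend Tables 20 and 21 as follows:

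1. Take interaction p-values from likelihood-ratio tests instead of Wald tests, using the Firth-penalised version where a cell is empty.
2. Report subgroup odds ratios by Firth logistic regression with profile-likelihood intervals, and use the same estimator for the overall odds ratio on that endpoint's forest plot so that estimators are not mixed.
3. As an alternative to item 2, where either arm has fewer than a set number of responders (eg, 3), mark the odds ratio NE and show only counts and the Miettinen-Nurminen difference.

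ACR20 can stay as planned. The cost is SAP wording and a few options in existing code, with no new data. The downsides are slight shrinkage of the odds ratios and intervals that stay very wide in sparse cells, as 0.43 to 965 for 0/8 versus 2/8 shows. That width is an honest picture of the information available. The plain likelihood-ratio test is also not exact in sparse data (up to 9.4% rejection in the simulations).
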